## 2.0 Background

Venous thromboembolism (VTE) refers to the formation of pathological blood clots in extremity veins (deep vein thrombosis, DVT) and/or pulmonary arteries (pulmonary embolism, PE). VTE is common, with an estimated incidence of 1-2 per 1000 in the general population, and increases to over 1% in the elderly. VTE is a considerable public health threat. Approximately 300,000-600,000 patients develop VTE in the United States each year, accounting for 60,000-100,000 deaths. According to the Healthcare Cost and Utilization Project, about 350,000 hospital admissions were due to VTE, costing over three billion dollars in 2011 alone. In addition, approximately one third of patients die within one year of their initial VTE, and one third of survivors suffer from long-term morbidity.

Anticoagulation is the current standard of care for acute VTE. However, even after a course of anticoagulation, 30% patients have VTE recurrence in 10 years after an unprovoked VTE, and 25-50% patients will develop post-thrombotic syndrome (PTS), causing long-term morbidity. Therefore, there is significant room for improvement. To accomplish this, it is crucial to have a better understanding of the pathophysiology of VTE and its complications. Although some important biomarkers in VTE were identified, the detailed hemostatic, inflammatory, and lipidomic biomarker profiles in patients after an acute VTE and their evolution and interplay in relation to treatments are unclear. A better understanding can help to identify promising targets to develop novel therapy.

The first aim of the study is to investigate important biomarkers in acute VTE as below:

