Serum phospholipids play crucial roles in inflammation and serve as the substrate for phospholipase A2 (PLA2), which subsequently liberates arachidonic acid for cyclooxygenase (COX) and lipoxygenase (LOX) to generate eicosanoids. In addition, these bioactive phospholipids play a major role in inflammation and repair. However, the quantification of these bioactive lipids and the process of their modulation of inflammation during acute VTE are unclear, and this study intends to clarify it. Lipid biomarkers of inflammation that will be analyzed in the study include free fatty acids and eicosanoids.

Statins are effective in the prevention of arterial thrombosis. Recently, arterial and venous thrombosis are shown to share common pathophysiological mechanisms, and effective therapies for arterial thrombosis could provide benefits in VTE. Several observational studies and the JUPITER trial, a large, randomized, placebo-controlled study, demonstrates that statins significantly reduce the risk of first VTE by 40-50%. Additionally, as few as 3 days of atorvastatin increase plasma fibrin clot permeability and susceptibility to lysis. These promising results, as well as their safety profiles, make statins an attractive potential addition to the standard anticoagulation for treating acute VTE, in an effort to reduce long-term morbidity.

Our second aim is to determine the actions of statins on the proposed biomarkers in acute VTE because: First, the effects of statins on thrombin generation in patients with acute VTE have not been studied. A study in patients with atrial fibrillation on warfarin showed a 40% reduction in endogenous thrombin potential with only three months of intensive cholesterol-lowering treatment including statins. Similar effects could be seen in patients with acute VTE. In addition, previous studies evaluating the effects of statins on the reduction of D-dimer or inflammatory cytokines revealed promising results but were not focused on patients with acute VTE. Therefore, this study will generate important information for acute VTE patients.

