## 6.0 Study calendar

	Initial visit	3 month 	9 month 
Singed informed consent	x		
Medical/treatment history	x	x	x
Physical examination	x	x	x
Vital signs	x	x	x
CBC with diff	x	x	x
Chemistry, including liver function tests	x	x	x
Fasting lipid profiles	x	x	x
hs-CRP	x	x	x
D-dimer	x	x	x
Urine <math>\beta</math>-hCG	x		
Thrombin generation assay	x	x	x
IL-6, IL-8, TNF-<math>\alpha</math>	x	x	x
Lipidomic profiles	x	x	x
Doppler ultrasound of bilateral lower extremities		x	
Prescription of statins	x	x	

All scheduled visits are allowed a window of +/- 21 days

CBC includes: white blood cells with differential, hemoglobin, red blood cells, and platelets

Chemistry and liver function tests include: sodium, potassium, carbon dioxide, glucose, BUN, creatinine, calcium, total protein, albumin, bilirubin, alkaline phosphatase, AST and ALT

Required only in women of child-bearing potential

Lipidomic profiles includes free fatty acids, lipoprotein-associated phospholipase A2, pro-inflammatory eicosanoids

Prescription of statins only in the statin arm

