## **9.0 Correlative Studies**

### **9.1 Laboratory Studies at Enrollment**

9.1.1 The initial laboratory tests will be obtained at the time of enrollment on this study. Blood will be collected after overnight fasting for at least 9 hours. Laboratory tests will include:

- CBC (complete blood count)
- chemistry panel (Na, K, Cl, CO2, Cr, BUN, Ca, and glucose),
- liver function tests (AST, ALT, ALP, total and direct bilirubin)
- D-dimer
- high-sensitivity C-reactive protein (hs-CRP)
- fasting lipid profiles (LDL, HLD, TG, total cholesterol)
- β-hCG is required only in women of child-bearing potential

*Research labs:*

- thrombin generation assay
- IL-6, IL-8, tumor necrosis factor (TNF)-α
- lipidomic profiles including free fatty acids, lipoprotein-associated phospholipase A2, pro-inflammatory eicosanoids
- plasma levels and RNA expression of tissue factor (TF), tissue factor pathway inhibitor (TFPI), and other clotting factors

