## **18.0 Lipidomic profiles**

18.1 Lipidomic profiles will be done in [name] laboratory. Blood samples for measurement of lipidomic profiles will be drawn in two vacutainer tubes, one containing 3.2% sodium citrate and the other being a serum separator tube.

After collection, blood will be separated into individual constituents including serum. Lipidomic profiles will be collected on blood samples using a triple quadrupole mass spectrometry platform called Lipidzyzer which is enabled through ion mobility hardware. This assay covers 13 different lipid classes and uses 56 stable isotope internal standards to provide quantitative results for as many as 1,100 lipid species. A separate LCMS panel will be utilized to determine eicosanoid profiles in blood. Both of these

assays will be conducted in the Nutrient & Phytochemical Analytic Shared Resource (NPASR) of the OSU Comprehensive Cancer Center under the direction of Acting Director, [name]..

**19.0 Plasma levels and RNA expression of tissue factor (TF), tissue factor pathway inhibitor (TFPI), and other clotting factors**

19.1 These tests will be done in [name] laboratory at BloodCenter of Wisconsin according to their standard protocol. The plasma samples will be frozen and stored at -80°C at the Ohio State University until the end of the study, when samples will be delivered to [name] lab to perform the research testing.

19.2 After plasma was removed from each tube as per protocol above, the buffy coats in the tubes will be collected as much as possible and stored in RNAlater® reagent as per manufacturer's protocol. These buffy coats will be used for analysis of RNA expression in [name] laboratory at the end of the study, according to their standard protocol.

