**20.0 Statistical Analysis**

At least 66 evaluable patients will be randomized (1:1 allocation, 33 evaluable patients in each arm) into "anticoagulation" versus "anticoagulation +atorvastatin" arms. The primary endpoints are thrombin peak and thrombin generation. Based on the published data, we anticipate an 80% power to detect an effect size of 0.7 standard deviations in the reduction of thrombin peak or thrombin generation between the two arms with two-side alpha of 0.05 using a two-sample t test. An overall alpha of 0.1 for this pilot study was split into 0.05 for each endpoint (thrombin peak and thrombin generation) using Bonferroni method. Considering possible drop-outs, our target enrollment will be 80 patients, with 40 on each arm.

All data will be collected on study-approved data collection forms and entered into Research Electronic Data Capture (REDCap), which is a secure, web-based application designed to support data capture for research studies by building and managing online surveys and databases. The system was built with the help of the OSU Research Informatics Services.

Descriptive statistics (i.e. means, standard deviations, 95% confidence intervals for continuous variables, and frequencies for discrete data) and graphical analyses will be used for all clinical outcomes, demographics, VTE related events, laboratory results, and adverse events for each arm. The secondary endpoints will be compared between the two arms using chi-square test or Fisher's exact test, whichever is appropriate. The associations between treatment type and the change in biomarkers will be evaluated using two-sample t test. Log-transform will be used if necessary. Linear mixed models will be used to study the associations between the primary endpoints and treatment, and trend across time. The interaction term "arm x time" will be included in the model to study whether the two treatment arms have different "behavior" across time. Potential confounders will be included in the models. Thrombin peak concentration and

endogenous thrombin potential at 9 months will be compared between the patients on anticoagulation and those off anticoagulation.

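### Section 20 tests change in biomarkers by t test with no multiplicity rule or exploratory label, and the number of lipid tests is undefined

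*Combined protocol and SAP*

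**What the plan says.** Objective 1.2.4 covers changes in hemostatic, inflammatory and lipidomic biomarkers at 3 and 9 months relative to enrollment. Section 20 supplies the comparison between arms: "The associations between treatment type and the change in biomarkers will be evaluated using two-sample t test", with log transformation if needed. Its only multiplicity statement is "An overall alpha of 0.1 for this pilot study was split into 0.05 for each endpoint (thrombin peak and thrombin generation) using Bonferroni method".

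The lipid measures are described in several places:

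- Section 2.0: "Lipid biomarkers of inflammation that will be analyzed in the study include free fatty acids and eicosanoids".
- Section 6.0, footnote 5: "Lipidomic profiles includes free fatty acids, lipoprotein-associated phospholipase A2, pro-inflammatory eicosanoids". Sections 9.1 and 9.2 give the same three items.
- Sections 9.1 and 9.2 also itemise a fasting lipid panel (LDL, HDL, triglycerides, total cholesterol), separately from the research lipidomics.
- Section 18.0: the platform covers 13 lipid classes and can "provide quantitative results for as many as 1,100 lipid species". It adds: "A separate LCMS panel will be utilized to determine eicosanoid profiles in blood". The size of that panel is not given.

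**The concern.** Lipoprotein-associated phospholipase A2 is a single analyte, but free fatty acids and eicosanoids are groups, and no individual member of either is named. The plan does not say which outputs of the two assays will be tested, how many there are, when the list is fixed, or which results are exploratory. Section 20 is careful about multiplicity for two endpoints and silent on what may be a much larger set.

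This matters because Section 2.0 gives the biomarker work a purpose: "A better understanding can help to identify promising targets to develop novel therapy". Without a stated number of tests or adjusted p-values, a reader of the results cannot judge how many of the lipids called significant would be expected by chance.

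A second point concerns the method. The t test on change does not make the best use of the enrollment value, which Section 9.1 already collects. With 33 evaluable patients per arm, precision is worth having.

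**Working it through.** **Inputs from Section 20.** 33 evaluable patients per arm; two-sided alpha 0.05, 0.7 SD and 80% power, all stated for the thrombin endpoints only.

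**Assumed inputs, not in the documents.** Alpha 0.05 for each lipid test; 3, 20, 200 or at most 1,100 analytes; 0.7 SD for affected lipids; the share of lipids affected; the correlation between enrollment and follow-up values; independent analytes unless stated.

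**The plan's own figure.** The exact two-sample t power at 33 per arm, 0.7 SD and alpha 0.05 is 0.7997, so the stated 80% reproduces. The overall alpha is 0.05 + 0.05 = 0.10, all of it used by the two thrombin endpoints.

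**Expected false positives if no lipid responds** (number of tests × 0.05, per time point):

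| Analytes tested | Expected false positives |
|---|---|
| 3 (the listed items as three measures) | 0.15 |
| 20 | 1 |
| 200 | 10 |
| 1,100 (assay ceiling) | 55 |

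Testing at both 3 and 9 months doubles these. Correlation among lipids leaves the expected count unchanged but widens its spread. For 200 null analytes in 13 blocks with within-block correlation 0.5, the simulated 95% range is 2 to 22, against 5 to 16 under independence.

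**Share of nominally significant lipids that are false.** With 200 analytes and 10% affected at 0.7 SD, expect 180 × 0.05 = 9 false and 20 × 0.80 = 16 true findings, and 9/25 = 0.36. The simulated mean proportion is 0.35. It is lower with few analytes, because runs with no findings count as zero. Simulated means at 0.7 SD, for 20 to 200 analytes:

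| Share affected | No adjustment | Benjamini-Hochberg 5% | Power per lipid: none → BH 5% |
|---|---|---|---|
| 10% | 0.29-0.35 | about 0.045 | 80% → 44-36% |
| 20% | 0.17-0.20 | about 0.04 | 80% → 52-48% |
| 50% | 0.05-0.06 | about 0.025 | 80% → about 65% |

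At the low end, with three measures of which one is affected, the false share is about 6% without adjustment and 3% with Benjamini-Hochberg at 5%. At 0.5 SD with 10% affected, power falls from 52% to 16-7%.

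**Baseline-adjusted model against change score.** Let k be the enrollment SD divided by the follow-up SD, and rho the correlation. In large samples the variance ratio is

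(1 − rho²) / (1 + k² − 2·rho·k).

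This is never above 1, because the denominator equals (1 − rho²) + (k − rho)².

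- k = 1: the ratio is (1 + rho)/2, that is 0.65, 0.75 and 0.85 for rho 0.3, 0.5 and 0.7.
- k = 0.5: 0.91/0.95 = 0.96, 0.75/0.75 = 1.00 and 0.51/0.55 = 0.93 for the same rho.

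With k = 1, 10% affected and Benjamini-Hochberg at 5%, power becomes 71-69%, 63-58% and 54-49% for rho 0.3, 0.5 and 0.7, against 44-36% with the change score. With k = 0.5 little or none of this is recovered.

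**The case against.** The strongest reply is that this is a pilot, that nothing here touches its primary conclusion, and that strict error control works against a search for targets: by the figures above, power per lipid may fall by about half. Labelling species-level results exploratory and reporting how many were tested would remove much of the harm. That stands, and it sets the severity. It does not justify leaving the number of tests undefined.

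Several stronger readings are tempting, and the documents do not support them:

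- *That no lipid analyte is named.* Lipoprotein-associated phospholipase A2 and the fasting panel are named individually. The gap concerns fatty acids, eicosanoids and the other species on the platform.
- *That 1,100 tests are planned.* That figure is what the assay can deliver. The 55 is a ceiling.
- *That the plan specifies unadjusted tests.* It is silent on both alpha and adjustment.
- *That the t test on change is invalid.* Under randomization it is valid; the issue is precision.

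Two further points are fair. Objective 1.2.4 is worded as change from enrollment in both arms, not as a contrast of arms. The contrast comes from Section 20 and from the second aim in Section 2.0, so descriptive changes within each arm should still be reported. The same silence also covers the cytokines, tissue factor, its inhibitor and the other clotting factors, so a rule for lipids alone would close only part of the gap.

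**Conclusion.** The point holds at low severity. Section 20 gives no significance level, multiplicity rule or exploratory label for the biomarker tests, and the lipid lists cannot be turned into a number of tests. The consequence depends on quantities that the plan does not fix. It is negligible if three measures are tested (0.15 expected false positives per time point). With 20 to 200 analytes of which 10% respond at 0.7 SD, about 29-35% of nominally significant lipids would be false. If half respond, the share is only 5-6%, and adjustment gains little. These figures assume alpha 0.05, 33 per arm and independent analytes; with block correlation 0.5 and 200 analytes, the 10% case gives 34% without adjustment and 4% with it.

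The baseline-adjusted model is the better method on precision, but its gain is assured only in the sense of no large-sample loss. It is material if the two SDs are similar and may be near zero if the enrollment SD is much smaller. The primary conclusion, sample size and patient safety are unaffected.

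**What to change.** Amend Section 20 before any lipid data are seen.

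1. **Method.** Replace the t test on change with a linear model for the 3- or 9-month value, with arm and the enrollment value as terms, on the log scale where needed. Do this for the lipids and preferably for all continuous biomarkers, so that they share one analysis. Keep descriptive changes from enrollment by arm for objective 1.2.4.
2. **Multiplicity.** Make the groups in Section 6.0, footnote 5, the secondary lipid family, itemised by analyte. Label every other species exploratory. Apply Benjamini-Hochberg within each family and time point at a stated false discovery rate. Report the number of tests with raw and adjusted p-values.

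The rate needs its own justification. The plan's overall alpha of 0.10 is a familywise rate over two endpoints, so it is no argument for a 10% false discovery rate. For comparison, at 0.7 SD with 10% of 20 to 200 analytes affected, a 10% rate gives power of 56-50% and a false share of about 9%; a 5% rate gives 44-36% and about 4.5%.

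The cost is an analyte list, a paragraph of text, a one-covariate model and an adjustment step. No new patients, visits or samples are needed. The real price is fewer lipids declared significant, which step 1 offsets in part.

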## 21.0 Costs of the Study

Given the fact that all patients will be receiving standard therapy for VTE (anticoagulation), either the patient or their insurance carrier will be responsible for all of the medical expenses associated with the treatment and follow up of their VTE. The costs associated with the research laboratory studies will be paid by the study researchers and will not be passed on to patients or their insurance carriers. The cost of atorvastatin will be reimbursed by the study researchers. Patients enrolled on this study will not incur any additional expenses as a result of enrolling on this protocol.

